#### **5.7.1** Device or Procedure-Related Adverse Events

Device or procedure-related adverse events are defined as adverse events that are adjudicated by the Clinical Events Committee as possibly, probably or definitely device and/or procedure-related, regardless of the temporal relationship to the MitraClip procedure. Device or procedure-related adverse events will be broken down into those that occur within 30 days of the procedure and those that occur after 30 days of the procedure. Examples of device-related adverse events are:

- Myocardial perforation
- Single Leaflet Device Attachment
- Embolization of the MitraClip device or MitraClip System components
- Iatrogenic atrial septal defect
- Mitral valve stenosis
- Need for mitral valve replacement instead of repair due at least in part to the MitraClip procedure or the presence of the MitraClip device

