8.3 Device or Procedure-Relationship

Determination of whether there is a reasonable possibility that the MitraClip device or MitraClip procedure caused or contributed to an AE is to be assessed by the Investigator and recorded on the appropriate eCRF form as not related, possibly related, probably related, definitely related or unknown. Determination should be based on assessment of temporal relationships, biologic plausibility, association (or lack of association) with underlying disease and/or presence (or absence) of a more-likely cause.

Definitions for determination of MitraClip device relationship include:

Not Related: Exposure to the MitraClip device has not occurred (no temporal relationship), or the occurrence of the adverse event is not reasonably related in time, or there is a definite alternative etiology, or it is biologically implausible for the adverse event to be related to the use of the device.

Possibly Related: Exposure to the MitraClip device has occurred; and it cannot be ruled out that the device is not responsible for the adverse event.

Probably Related: Exposure to the MitraClip device has occurred or the adverse event is reasonably related in time; and the device is more likely than other alternative causes to be responsible for the adverse event.

Definitely Related: Exposure to the MitraClip device has occurred or the adverse event is related in time; and the device is definitely responsible for the adverse event.

Unknown Exposure to the device and the occurrence of adverse event cannot be reasonably determined to be unrelated to the device. If the relationship is identified as unknown it will be treated as related to the device.

Determination of MitraClip procedure relationship includes assessment of AEs for relationship to any of the following: discontinuation of medications for the MitraClip procedure, administration of local or general anesthesia, or the MitraClip procedure. Relationship of MitraClip procedure will be assessed regardless of the temporal relationship to the MitraClip procedure.

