10.4 Clinical Events Committee

The Clinical Events Committee (CEC) is a multi-disciplinary team comprised of qualified physicians who are not investigators in the trial. The composition, guiding policies, and

operating procedures governing the CEC are described in a separate **CEC Manual of Operations**. The CEC will review and adjudicate pre-specified events reported by trial investigators or identified by the Safety & Surveillance personnel/designate for the trial as documented in CEC Manual of Operations (MOPs). Every effort will be made to blind the CEC to the subject's treatment assignment.

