APPENDIX A: Definitions

The following definitions will be used in the COAPT Clinical Investigational Plan. All events constituting primary or secondary endpoints will be adjudicated by the independent Clinical Events Committee (except embolization, which will be site reported, and Mitral Valve Stenosis and SLDA, which will be assessed by Echocardiography Core Lab), along with relationship to the MitraClip device or procedure.

ATRIAL FIBRILLATION (AF) – Heart Rhythm Society Guidelines

Paroxysmal: Recurrent (≥ 2) atrial fibrillation episodes that terminate spontaneously within 7 days.

Persistent: Atrial fibrillation that is sustained beyond 7 days, or lasting less than 7 days but necessitating pharmacologic or electrical cardioversion.

Longstanding Persistent AF: Continuous atrial fibrillation of greater than 1 year duration.

Permanent: Atrial fibrillation in which cardioversion has failed or not been attempted.

CARDIOVASCULAR DEATH (VARC)

Cardiovascular death is defined by the Valve Academic Research Consortium (VARC)¹⁹ as any one of the following:

- Any death due to proximate cardiac cause (e.g. MI, cardiac tamponade, worsening heart failure)
- Unwitnessed death and death of unknown cause
- All procedure-related deaths, including those related to a complication of the procedure or treatment for a complication of the procedure
- Death caused by non-coronary vascular conditions such as cerebrovascular disease, pulmonary embolism, ruptured aortic aneurysm, dissecting aneurysm, or other vascular disease

¹⁹ Leon MB, Piazza N, Nikolsky E, et al. Standardized endpoint definitions for transcatheter aortic valve implantation clinical trials: a consensus report from the Valve Academic Research Consortium. *J Am Coll Cardiol* 2011;57:253-269.

DEVICE OR PROCEDURE RELATED ADVERSE EVENT

Adverse events that are adjudicated by the Clinical Events Committee as probably, possibly or definitely device and/or procedure related, regardless of temporal relationship to the MitraClip procedure. For events reported by the site that are not adjudicated by the Clinical Events Committee, the device relationship will be reported based on site reports.

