#### 1 Introduction

This document contains the Statistical Analysis Plan (SAP) for the COAPT Trial, protocol 11-512. This plan is based on the Version 8.0, October 12, 2016 study protocol.

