#### 5 Statistical Methods

#### 5.1 Randomization and Blinding

Subjects will be randomized in a 1:1 ratio to the Device or Control groups. Randomization will be stratified by site and cardiomyopathy etiology (ischemic or non-ischemic). Randomization will be performed using permuted blocks (random block sizes) and block

sizes will not be revealed to sites. The Electronic Data Capture system will be used to randomize subjects.

The subject, some site personnel and some Sponsor personnel will be aware of treatment assignment. Sponsor statisticians will not have access to any data that combines outcomes with treatment assignment prior to performing the final analysis. No Sponsor personnel will have access to outcome data summarized by treatment until the primary endpoint analysis is complete. All events constituting primary or secondary endpoints will be adjudicated by the independent Clinical Events Committee (except embolization, which will be site reported, and MV Stenosis and SLDA, which will be assessed by the Echocardiography Core Lab), along with relationship to the MitraClip device or procedure. Every effort will be made to blind the Clinical Events Committee (CEC) to the subject's treatment assignment.

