#### 5.5 Analysis of Safety

#### 5.5.1 Primary Safety Endpoint

A composite of device related complications including Single Leaflet Device Attachment (SLDA), device embolizations, endocarditis requiring surgery, Echocardiography Core Laboratory confirmed mitral stenosis requiring surgery, LVAD implant, heart transplant, or any device related complications requiring non-elective cardiovascular surgery at 12 months will be the primary measure of safety.

All events constituting the primary safety endpoint will be adjudicated by the independent Clinical Events Committee (except embolization, which will be site reported, and Mitral Valve Stenosis and SLDA, which will be assessed by the Echocardiography Core Lab). SLDA is defined as unilateral MitraClip detachment from one leaflet, as assessed by the Echocardiography Core Laboratory as definite. In the case of MV surgery, SLDA can also be identified by operating physician.

The analysis of the primary safety endpoint is a test of the proportion of subjects free from the composite of safety events in the Device group at 12 months to a pre-specified performance goal of 88%.

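### SAP 5.7.1 counts related adverse events by CEC adjudication alone and omits the protocol's fallback to site-reported relationship, so the table can undercount if the SAP is followed literally

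*SAP*

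**What the plan says.** SAP 5.7.1 defines the endpoint as "adverse events that are adjudicated by the Clinical Events Committee as possibly, probably or definitely device and/or procedure-related", with no other route into the count, and splits it at 30 days after the procedure. Protocol 4.5.1 and 7.6.1 carry the same definition. All three sections list six examples, among them SLDA, embolization, mitral stenosis, iatrogenic atrial septal defect and myocardial perforation.

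Four other rules bear on the same count:

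- Protocol Appendix A, defining the same term, adds: "For events reported by the site that are not adjudicated by the Clinical Events Committee, the device relationship will be reported based on site reports". The SAP does not repeat this, although its Introduction says "This plan is based on the Version 8.0, October 12, 2016 study protocol".
- Protocol 10.4 limits what the committee sees: "The CEC will review and adjudicate pre-specified events reported by trial investigators". The list is in a separate manual of operations.
- SAP 5.1 has the CEC adjudicate primary and secondary endpoint events, "except embolization, which will be site reported, and MV Stenosis and SLDA, which will be assessed by the Echocardiography Core Lab), along with relationship". The closing clause refers to whether the event is tied to the clip or its placement. Appendix A has the same sentence. SAP 5.5.1 repeats the exception for the primary safety endpoint, "except embolization, which will be site reported, and Mitral Valve Stenosis and SLDA, which will be assessed by the Echocardiography Core Lab", without the relationship clause.
- Protocol 8.3 gives the investigator's relationship scale, which has a fifth category: "If the relationship is identified as unknown it will be treated as related to the device".

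**The concern.** One term has two working definitions. Under SAP 5.7.1 an event counts only if the CEC has adjudicated it as related. Under Appendix A, an event that never reached the CEC still counts on the site's call. A programmer working from the SAP would apply the first rule and drop site-attributed events that the protocol says to report.

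Two further points are left open. The SAP does not name who judges relatedness for SLDA, stenosis and embolization, which the CEC does not itself ascertain. Nor does it map a site answer of *unknown*.

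At stake is the completeness of a descriptive table of device and procedure harm. Any omission under the literal rule can only lower the count, and the choice between definitions would be left to whoever programs the table.

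**Working it through.** The plan states no rate, sample size or power for this endpoint, so there is no figure to reproduce. The check is a comparison of rules, followed by a bound for the one event type with a usable planning rate.

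**How each kind of event is treated**

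| Event | SAP 5.7.1 read literally | Protocol Appendix A, with 8.3 |
|---|---|---|
| CEC adjudicates it as possibly, probably or definitely related | Counted | Counted |
| Not sent to the CEC; site calls it possibly, probably or definitely related | Not counted | Reported on the site's call |
| Not sent to the CEC; site calls device relationship *unknown* | Not counted | Treated as device-related |
| Site-reported embolization | Counted only if the CEC judges relationship | CEC's call or, failing that, the site's |
| Core-laboratory SLDA or stenosis | Counted only if the CEC judges relationship | CEC's call or, failing that, the site's if the site reported the event; otherwise not stated |

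The second and third rows are where the rules differ outright. The last two depend on whether the exception in SAP 5.1 covers only finding the event or also judging its relationship.

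**Bound for SLDA**

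Inputs: SLDA rate 4% at 12 months (SAP Table 1) and 305 Device subjects (SAP 5.8.1).

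- Lower bound: 0, if the CEC judges relatedness, or if the Appendix A fallback is applied and core-laboratory findings are counted.
- Upper bound: 0.04 × 305 = 12.2, about 12 subjects, if no SLDA passes the CEC-only rule.

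**Adding embolization and stenosis**

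Table 1 assumes less than 0.1% for each. At the 0.1% ceiling, (0.04 + 0.001 + 0.001) × 305 = 12.81, so the worst case for the three types is about 12 to 13 subjects, or 4.0% to 4.2%. The Table 1 stenosis rate is for stenosis requiring surgery, whereas SAP 5.7.1 lists stenosis without that condition. The 12.81 is therefore not a ceiling for stenosis of every kind.

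**Other events**

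Iatrogenic atrial septal defect and myocardial perforation are not themselves primary or secondary endpoints. Whether the CEC sees them depends on its manual, and the documents give no rate for related events outside its list. This part cannot be quantified.

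**The case against.** The strongest reply is that nothing need be lost, and parts of it stand.

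- **Relationship may stay with the CEC.** The exception in SAP 5.1 and Appendix A is in parentheses, and the relationship clause follows it. It is reasonable to read the core laboratory and sites as establishing that the event occurred and the CEC as judging relatedness. SAP 5.7.1 also names SLDA, embolization and stenosis as examples. A reader might infer that these three can never qualify under 5.7.1; the documents do not support that. But the clause covers only events that constitute primary or secondary endpoints, so stenosis not requiring surgery, for instance, remains unaddressed.
- **The fallback is still in the protocol.** The SAP rests on that protocol and nothing revokes the Appendix A sentence. A reader might therefore infer too much in saying that the reported rate *is* too low; the sentence assigning events to sites is the rule by which they are reported. What remains is that Protocol 4.5.1 and 7.6.1 and SAP 5.7.1 all omit it, and the SAP governs the programming.
- ***Unknown* is on another assessor's scale.** Protocol 8.3 describes the investigator's form, and the CEC's scale is not in these documents. So this is an unmapped category, not a direct contradiction, and the rule concerns device relationship only.
- **The harms appear elsewhere.** SLDA and embolization are in the primary safety composite. SAP 5.7.4 reports its components and device-related complications through 5 years, and has rows for stenosis and for septal defects needing intervention. SAP Appendix A.1 includes site-reported cardiac perforation. This table is not the only view of device harm.
- **The endpoint is descriptive.** SAP 5.7 says so, and Protocol 4.5 ties labeling claims to primary and secondary endpoints. This stands in full.

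**Conclusion.** The inconsistency is real and should be resolved, but it shows a risk of undercounting and not a demonstrated undercount. SAP 5.7.1 and Protocol 4.5.1 and 7.6.1 give a CEC-only rule; Appendix A gives a broader one for the same term. The source of the relationship call for core-laboratory and site-determined events, and the handling of *unknown*, are not stated.

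For SLDA the possible loss is 0 to about 12 of 305 Device subjects. That range assumes the Table 1 rate at 12 months, the full planned Device group and one count per subject; where the truth falls depends on which reading is applied. The effect for other events is unknown. No hypothesis test, success criterion or primary safety result changes.

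**What to change.** In SAP 5.7.1:

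1. Carry over the Appendix A sentence, so that events not adjudicated by the CEC are counted when the site calls them possibly, probably or definitely related. Count a site answer of *unknown* for device relationship, as Protocol 8.3 provides, without extending it to procedure relationship.
2. Name who makes the relationship call for core-laboratory SLDA and stenosis and for site-reported embolization, limited to subjects who underwent a MitraClip procedure. The limit matters because Protocol Appendix A defines stenosis by valve area alone and SAP 5.7.3 reports valve area in both groups. Counting every core-laboratory stenosis as related could bring in a Control subject who never received a clip.
3. Report CEC-adjudicated and site-assessed events separately within the existing 30-day split.

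Align Protocol 4.5.1 and 7.6.1 with Appendix A.

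The cost is wording and a programming rule. Sites already record relationship on the eCRF (Protocol 8.3), so no new data collection appears necessary. The downside is that the reported related-event rate may be slightly higher and will rest partly on site assessment that is not blinded; separate reporting makes that visible.

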#### 5.7.2 Device and Procedure-Related Endpoints

The following device and procedure-related acute endpoints will be reported for the Device group:

- Implant Rate: defined as the rate of successful delivery and deployment of MitraClip device with echocardiographic evidence of leaflet approximation and retrieval of the delivery catheter
  - Any additional MitraClip device implantation after the index procedure will be summarized and reported as an additional MitraClip device intervention and will be further reported as a device or procedure failure, if appropriate.
- Device Procedure Time: defined as the time elapsed from the start of the transseptal procedure to the time the Steerable Guide Catheter is removed
- Total Procedure Time: defined as the time elapsed from the first of any of the following: intravascular catheter placement, anesthesia or sedation, or transesophageal echocardiogram (TEE), to the removal of the last catheter and TEE.
- Device Time: defined as the time the Steerable Guide Catheter is placed in the intraatrial septum until the time the MitraClip Delivery System (CDS) is retracted into the Steerable Guide Catheter.
- Fluoroscopy duration: defined as the duration of exposure to fluoroscopy during the MitraClip procedure

#### 5.7.3 Echocardiographic Endpoints

The following echocardiographic endpoints will be reported for the Device and Control groups at baseline, discharge (or 30 days if discharge echocardiogram is not available), 6 months, 12 months, 24 months and then yearly through 5 years. For continuous variables, change from baseline to each follow-up will also be reported:

- MR Severity GradeEffective Regurgitant Orifice Area
- Regurgitant Volume

- Regurgitant Fraction
- Left Ventricle End Diastolic Volume (LVEDV)
- Left Ventricular End Systolic Volume (LVESV)
- Left Ventricular End Diastolic Dimension (LVEDD)
- Left Ventricular End Systolic Dimension (LVESD)
- Left Ventricular Ejection Fraction (LVEF)
- Right Ventricular Systolic Pressure (RVSP)
- Mitral Valve Area
- Mean Mitral Valve Gradient
- Systolic Anterior Motion of the mitral valve (present or absent)
- Cardiac Output
- Forward Stroke Volume

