4.5.3 Echocardiographic Endpoints

The following echocardiographic endpoints will be reported for the Device and Control groups at baseline, discharge (or 30 days if discharge echocardiogram is not available), 6 months, 12 months, 24 months and then yearly through 5 years. For continuous variables, change from baseline to each follow-up will also be reported:

- MR Severity Grade
- Effective Regurgitant Orifice Area
- Regurgitant Volume
- Regurgitant Fraction
- Left Ventricle End Diastolic Volume (LVEDV)
- Left Ventricular End Systolic Volume (LVESV)
- Left Ventricular End Diastolic Dimension (LVEDD)
- Left Ventricular End Systolic Dimension (LVESD)
- Left Ventricular Ejection Fraction (LVEF)
- Right Ventricular Systolic Pressure (RVSP)

- Mitral Valve Area
- Mean Mitral Valve Gradient
- Systolic Anterior Motion of the mitral valve (present or absent)
- Cardiac Output
- Forward Stroke Volume

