6.9.7 Procedural and Discharge Data

The following MitraClip procedural information should be recorded on the appropriate eCRF(s) after implant or attempted implant of the MitraClip device:

- General procedure information
- MitraClip implant information
- Laboratory and clinical tests
- Antiplatelet/Anticoagulation medications
- Concomitant cardiovascular medications
- Fluoroscopy duration
- Adverse events
- Protocol deviations
- Device deficiency

At the Discharge visit (Discharge occurs when subject leaves the implanting hospital), the following required tests and procedures should be completed (> 16 hours post MitraClip procedure and no later than day of discharge) as outlined below, and the information should be captured on the appropriate eCRFs:

- 12-lead ECG
- Blood draw
- Brief physical exam including vital signs (weight, heart rate, blood pressure and temperature)
- Echocardiogram (TTE) - discharge TTE must be performed at least 16 hours post MitraClip procedure and no later than 24 hours post-discharge

- Modified Rankin Scale
- Adverse events
- Protocol deviations
- Device deficiency

Instructions for the TTE are provided in this investigational plan and are located in **APPENDIX B: Echocardiography Protocol.**

6.10 “Treatment” Visit (Control Group)

The “Treatment” visit in the Control group must occur between 1 and 14 days after randomization. At the “Treatment” visit, Control group subjects will be seen by the HF specialist investigator, and will undergo a physical exam, including vital signs, cardiac health status and evaluation of heart failure medications.

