After the “Treatment” visit, the investigational sites will be provided the target date and required follow-up window time-frames for each subject in the electronic data capture system. Follow-up windows are summarized in **Table 1: Follow-up Schedule* and Windows for Registered Subjects**. All data required for follow-up must be collected within the window for that scheduled visit, and not necessarily on the same day.

Table 1: Follow-up Schedule* and Windows for Registered Subjects

| Follow-Up Visit | Window Start Day | Target Day | Window Close Day | Follow up Method |
|----------------------------------|------------------|----------------|------------------|---------------------------|
| Discharge (Device group only) | NA | Discharge date | NA | In hospital or Site visit |
| 1 Week (-1 /+3 days) | 6 | 7 | 10 | Phone contact |
| 30 Days (-3 /+14 days) | 27 | 30 | 44 | Site visit |
| 6 Months (±30 days) | 152 | 182 | 212 | Site visit |
| 12 Months (-14/+30 days) | 351 | 365 | 395 | Site visit |
| 18 Months (±30 days) | 518 | 548 | 578 | Site visit |
| 24 Months (±30 days) | 701 | 731 | 761 | Site visit |
| 3 Years (±45 days) | 1051 | 1096 | 1141 | Site visit |
| 4 Years (±45 days) | 1416 | 1461 | 1506 | Site visit |
| 5 Years (±45 days) | 1781 | 1826 | 1871 | Site visit |

* Follow-up visit dates are calculated from the “Treatment visit” for randomized subjects and from the index procedure for roll-in subjects

Echocardiography images (TTE) obtained at each follow-up visit should be submitted to the Sponsor in a timely manner. The ECL will provide feedback to sites regarding quality of images obtained.

During the follow-up period, if a subject requires a cardiac procedure (i.e. MV surgery, permanent LVAD, heart transplant, additional MitraClip procedure, etc.) which may or may not result in explant of the MitraClip device, the subject will remain in the trial and continue to be followed.

Subjects who do not have a scheduled follow-up visit will be documented as having a missed visit and a Protocol Deviation will be completed. The investigator will keep a record of

documented follow-up attempts in the subject's study file. Refer to Section **10.10 Protocol Deviations** for additional information.

Table 2 provides a complete listing of required tests and procedures for all subjects through the trial follow-up period.

Table 2: Clinical Evaluation Schedule for Registered Subjects

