| Items | Screening/ Baseline | Randomization Assignment (For randomized Subjects only) | Treatment Visit (Control Group) | Treatment Visit (Device Group or Roll-in) | Discharge (Device Group or Roll-in) | 1-Week Phone Contact | 30-Days ^d , 6, 12, 18, 24 Months | 3, 4, 5 Years |
|--|---|--|---------------------------------------|--|--|----------------------------|---|------------------|
| Informed Consent | X | | | | | | | |
| Medical History | X within 90 days pre-registration | | | | | | | |
| Evaluation by Local Heart Team including HF Specialist Investigator and CT Surgeon Investigator (in-person consult with HF specialist and CT Surgeon investigators is required). | X within 90 days pre-registration | | X | | | | X | X |
| Components of Frailty Index | X within 14 days pre-registration | | | | | | | |
| STS Risk Score | X within 90 days pre-registration | | | | | | | |
| Modified Rankin Scale ^a | X within 14 days pre-registration | | | | X | | X not required after 12-month visit | |
| Physical Examination & Vital Signs: (height (at Baseline only), weight, heart rate, blood pressure and temperature) | X within 14 days pre-registration | | X | X within 24 hours pre- procedure | X | | X | X |
| Concomitant Cardiovascular Medications | X | | X | X | X | | X | X |
| 12-lead ECG | X within 90 days and 14 days pre- registration | | | X within 24 hours pre- procedure | X | | X | X |
| Transthoracic Echocardiogram ^b | X within 90 days pre-registration | | | | X | | X | X |

| Items | Screening/ Baseline | Randomization Assignment (For randomized Subjects only) | Treatment Visit (Control Group) | Treatment Visit (Device Group or Roll-in) | Discharge (Device Group or Roll-in) | 1-Week Phone Contact | 30-Days ^d , 6, 12, 18, 24 Months | 3, 4, 5 Years |
|---|--|--|---------------------------------------|--|--|----------------------------|---|--------------------------------------|
| Transesophageal Echocardiogram | X within 180 days pre-registration | | | X within 3 days pre- procedure | | | | |
| Albumin | X within 14 days pre-registration | | | | | | | |
| CBC with differentials and platelet count Serum Creatinine PTT or PT or INR CK, CK-MB | X within 14 days pre-registration | | | | X | | X | |
| BNP or NT-proBNP ^c | X within 90 days pre-registration | | | | | | X | |

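### The first post-baseline echo column sets Device values from hospital discharge beside Control values from day 27 to 44

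*SAP*

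**What the plan says.** SAP 5.7.3 lists 15 echocardiographic measures (MR grade, regurgitant measures, LV volumes and dimensions, LVEF, RVSP, valve area and gradient, systolic anterior motion, cardiac output, forward stroke volume). After baseline, the first time point is "discharge (or 30 days if discharge echocardiogram is not available"; the next is 6 months. Change from baseline is also to be reported for continuous measures. Protocol 4.5.3 applies the same rule to both arms: "The following echocardiographic endpoints will be reported for the Device and Control groups at baseline, discharge", with the same 30-day fallback. Protocol 7.6.3 repeats it.

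The visit schedule in the protocol differs by arm at this point:

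- Table 1 (section 6.11) labels the discharge row "Discharge (Device group only".
- Table 2 marks a TTE under "Discharge (Device Group or Roll-in" and none under the Control Treatment visit.
- Section 6.9.7 sets the Device timing: "discharge TTE must be performed at least 16 hours post MitraClip procedure and no later than 24 hours post-discharge".
- Section 6.10 describes the Control Treatment visit: subjects "will undergo a physical exam, including vital signs, cardiac health status and evaluation of heart failure medications". No echo is included.
- Section 6.11.2 and Table 2 require a TTE at 30 days in all subjects. Table 1 gives that visit as "30 Days (-3 /+14 days" days, that is, day 27 to 44.

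**The concern.** The 30-day fallback reads like a rule for the occasional missing discharge echo. For Controls it is the only possible source, because no discharge echo exists for any of them. For Device subjects the discharge echo takes precedence whenever there is one. Their 30-day TTE then has no place in SAP 5.7.3, which does not list 30 days as a time point of its own.

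The resulting table has one column, one label and two arms, but the arms are measured at different times after the Treatment visit. A reader would naturally take it as an early side-by-side view of the arms. For LV volumes, LVEF, RVSP, gradient, output and stroke volume, any difference in that column combines the device effect with the difference between an immediate post-procedure state and a state some weeks later. The plan aligns the arms elsewhere. Protocol 10.14.2 says the schedule after the Treatment visit is the same in both groups, and NYHA class, 6MWD and KCCQ are all reported at 30 days in both arms.

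**Working it through.** The documents give no sample size, power or effect figure for this time point, so there is no plan figure to reproduce. The check compares visit timing.

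**Common clock.** The Table 1 footnote says "Follow-up visit dates are calculated from the" Treatment visit for randomized subjects. For the Device arm that is the procedure, so both arms count from day 0 of the same kind.

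**Which echo each subject contributes under SAP 5.7.3:**

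| Subject | Discharge TTE? | Value used | Time from Treatment visit |
|---|---|---|---|
| Control | Never scheduled | 30-day TTE | Day 27 to 44 |
| Device, discharge TTE present | Yes | Discharge TTE | From 16 hours; upper limit tied to discharge |
| Device, discharge TTE missing | No | 30-day TTE | Day 27 to 44 |

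**Gap between arms** = day of Control echo minus day of Device echo. The Control day is 27 (window opens), 30 (target) or 44 (window closes). The day of discharge is not stated, so the Device day is an assumed range:

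- Earliest permitted, 16/24 = 0.67 day: 27 − 0.67 = 26.3; 30 − 0.67 = 29.3; 44 − 0.67 = 43.3 days
- Day 1: 27 − 1 = 26; 30 − 1 = 29; 44 − 1 = 43 days
- Day 2: 27 − 2 = 25; 30 − 2 = 28; 44 − 2 = 42 days
- Day 7: 27 − 7 = 20; 30 − 7 = 23; 44 − 7 = 37 days

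Across discharge on day 1 to 7, the gap at target is 29 down to 23 days. No discharge day in that range brings the arms together.

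**Within the Device arm.** The same subtraction applies between Device subjects with and without a discharge echo. One Device summary could therefore hold values 26 to 43 days apart (discharge echo on day 1).

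**After the change.** With the 30-day TTE used in both arms, both are measured in the day 27 to 44 window, and the target gap is 30 − 30 = 0 days.

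**What is already aligned.** SAP 5.7.4 separately reports an MR-grade proportion (printed as < 2+) at 30 days in both arms. None of the other measures in SAP 5.7.3 has a time-aligned summary before 6 months.

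**The case against.** The strongest reply is that little rests on this column. SAP 5.7 makes these endpoints descriptive. SAP 5.7.3 says they will be reported by arm and names no difference, test or p-value, whereas SAP 5.7.4 says explicitly that changes from baseline will be compared between groups. Protocol 4.5 ties labeling claims to the primary and secondary endpoints. The two secondary echo endpoints, MR severity and LVEDV change, are assessed at 12 months on the same schedule in both arms. All of this stands, and it sets the severity.

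A reader might infer more than the documents support, in three ways:

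- **That the plan contains a biased early treatment comparison.** It specifies no between-arm analysis at this time point. The comparison is one that a reader would make from the table.
- **That the echo values are distorted by a known amount.** The documents give no figure for how any measure drifts in Controls over 30 days. Drift may be modest: the qualifying TTE follows stabilization on therapy (protocol 6.3.2.1), and baseline medications continue unless a change is clinically necessary (protocol 6.11.2). The time gap can be calculated; its effect on any echo measure cannot.
- **That survival selection is a material part of the problem.** Any visit-based echo summary is limited to subjects who are alive and attend. The documents do not say how early Device deaths fall before or after the discharge TTE. Moving both arms to 30 days would still condition on surviving to that visit. The point is therefore about timing alone.

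The documents also do not say that Device echoes are typically on day 1, or how complete discharge echoes will be. Those remain assumptions.

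What the reply does not answer is the rule itself. As written, it assigns non-concurrent values to the two arms under one label, although concurrent values are collected.

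**Conclusion.** The mismatch follows from the stated rule and the visit schedule; no missing detail has to be supplied to reach it. Every Control value in the first post-baseline column comes from day 27 to 44, and a Device value comes from discharge whenever a discharge echo exists. The size is a gap of roughly three to six weeks, conditional on an assumed discharge between day 1 and day 7. The effect on any individual echo measure cannot be quantified from the documents.

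Severity is minor. The consequence is confined to one early descriptive column, chiefly for the measures other than MR grade. It is still worth correcting, because the column is easily misread and the data for an aligned one are already required.

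**What to change.** In SAP 5.7.3 and protocol 4.5.3 and 7.6.3 (and the matching line in the protocol's trial summary):

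1. List 30 days as its own time point for both arms, using the 30-day TTE, followed by 6 months and the later visits as now.
2. Report the discharge TTE as an acute result for the Device group only, in the way SAP 5.7.2 already handles other acute measures.
3. Delete the fallback, so that a missing discharge echo is shown as missing and is not replaced by the 30-day echo.

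The cost is wording and one extra column in the tables. No new visit, imaging, data field or sample size is needed, and no primary or secondary analysis changes.
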